6.2 General principles

In general, descriptive statistics will be presented for all effectiveness variables and safety variables, as appropriate. Continuous variables will be summarised by descriptive statistics (sample size [n], mean, standard deviation, minimum, median, and maximum value) by treatment group. Categorical data will be summarised in frequency tables showing number of patients, frequency and percentage of occurrence by treatment group.

Graphical presentations will be used, as appropriate and individual patient data will be listed.

6.2.1 Missing data

In general imputation of missing observations will not be performed. Missing data will be reported descriptively.

6.2.2 Multiple comparisons

No adjustment for multiple comparisons will be made.

6.2.3 Treatment group comparisons

NA This is a Post Marketing Observational Study analyzing only one treatment group

6.2.4 Derived variables

For endpoints which are of index type (sums of sub-item scores) the CRF sometimes provide space where investigator can register the sum of sub-item scores. If QC process finds inconsistencies between sub-items and investigators total score the total score can be set to missing by the QC process.

It has been decided to disregard the investigators derived sums of sub-item scores and instead calculate these in the analysis database.

For information about derived analysis endpoints please see sections 5.1 and 5.2.

6.3 Study population results

Characteristics of patients prior to the start of dosing will be tabulated. The characteristics that will be summarised for baseline include subject demographics, disease characteristics including medical history, and prior and concomitant medications.

6.3.1 Disposition

The number and percentage of patients that reached the various stages of the study (e.g. enrolled, completed study). Reason for withdrawal will be listed. The number and percentage of patients in the different patient population analysis sets (FAS, PP, Safety) will also be tabulated.

6.3.2 Medical history

Concurrent illness and medical history will be reported as a listing for all enrolled patients.

6.3.3 Demographics and baseline patient characteristics

Demographics (gender, age, length, weight, BMI, ethnic background and smoking) will be presented as a table for the baseline visit.

6.4 Effectiveness analyses

Effectiveness analyses will be based on the Full analysis Set (FAS), as described in earlier sections, using paired samples t-tests or non-parametric methods such as Wilcoxon signed rank test as appropriate for numerical endpoints. Dichotomous response variables which will be analysed descriptively presenting proportion of responders with binomial exact 95% confidence interval.

The PP analysis set will be used as sensitivity analysis for the primary effectiveness endpoint.

6.5 Safety analyses

Responses to the CRF question "Has any SAE(s) occurred since last visit?" will be summarized descriptively for the 4, 12 and 24 week visits.

7 Changes of Analyses from Protocol

It was specified in Protocol that HiSCR was to be analyzed using t-test or non-parametric methods such as Wilcoxon signed rank-test.

HiSCR is a dichotomous response variable which will be analysed descriptively presenting proportion HiSCR with binomial exact 95% confidence interval.

It was specified in Protocol that HSIA and EQ5D was to be analyzed using t-test or non-parametric methods such as Wilcoxon signed rank-test.

No total scores for HSIA or EQ5D will derived. Both endpoints will be analyzed descriptively presenting result by sub-item. The EQ5D VAS score has however been added as one variable to be analysed using paired samples t-tests or non-parametric methods such as Wilcoxon signed rank test as appropriate

8 References

The numbered references present in section 1 Introduction are found in the Study protocol.

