11.1.2 Severity

The following definitions will be used to rate the severity for any adverse event being collected as an endpoint/data point in the study and for all serious adverse events.

Mild: The adverse event is transient and easily tolerated by the patient.

abb∨ie	Adalimumab P15-692 Protocol	
Moderate:	The adverse event causes the patient discomfort and interrupts the patient's usual activities.	
Severe:	The adverse event causes considerable interference with the patient's usual activities and may be incapacitating or life threatening.	

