11.1.3 Relationship to Pharmaceutical Product

The following definitions will be used to assess the relationship of the adverse event to the use of product:

Reasonable Possibility	An adverse event where there is evidence to suggest a causal relationship between the product and the adverse event.
No Reasonable Possibility	An adverse event where there is no evidence to suggest a causal relationship between the product and the adverse event.

If no reasonable possibility of being related to product is given, an alternate etiology must be provided for the adverse event.

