11.1.4 Serious Adverse Event Collection Period

Serious adverse events will be reported to AbbVie from the time the physician obtains the patient's authorization to use and disclose information (or the patient's informed consent) until 30 days or 5 half-lives following the intake of the last dose of physician-prescribed treatment.

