11.1.5 Serious Adverse Event Reporting

In the event of a serious adverse event, and additionally, any non-serious event of malignancy in patients 30 years of age and younger, whether related to study drug or not, the Investigator will notify the AbbVie contact identified in section 11.1.5 within 24 hours of the site being made aware of the event by entering the serious adverse event or non-serious event of malignancy in patients 30 years of age and younger data into the electronic data capture (EDC) system. Serious adverse events and non-serious events of malignancy in patients 30 years of age and younger, that occur prior to the site having

access to the EDC system or if the EDC system is not operable should be faxed/e-mailed to the AbbVie contact identified in section 11.1.5 within 24 hours of being made aware of the adverse event.

In the event of a serious adverse event, the physician will:

- For events from patients using and AbbVie product notify the AbbVie contact person identified below within 24 hours of the physician becoming aware of the event.
- For events from patients using a comparator product notify the Marketing Application Holder (MAH) for the comparator product within 24 hours of the physician becoming aware of the event.

Contact details for event reporting:

E-mail:		
Phone:		
Fax:		

As the safety profile of Adalimumab is stable and well established, non-serious events will not be actively solicited as these events are not likely to further contribute to the understanding of the safety profile of the product. Any non-serious reports will be collected as spontaneous reports if notified to AbbVie.

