5.3 Safety endpoints

• Non-serious Adverse events

As the safety profile of Adalimumab is stable and well established, non-serious events will not be actively solicited as these events are not likely to further contribute

to the understanding of the safety profile of the product. Any non-serious reports will be collected as spontaneous reports if notified to AbbVie.

• Serious Adverse events

Serious adverse events will be reported to AbbVie from the time the physician obtains the patient's authorization to use and disclose information (or the patient's informed consent) until 30 days or 5 half-lives following the intake of the last dose of physician-prescribed treatment.

In the CRF the response to the following question is registered at 4, 12 and 24 week visits:

Has any SAE(s) occurred since last visit?

6 Analysis Methods

The final statistical analyses will be performed at Scandinavian Development Services AB, Danderyd, Sweden by using the SAS ® version 9.3 or higher.

Continuous variables will be summarized using descriptive statistics (n, mean, SD, min, median, max). Categorical variables will be summarized in frequency tables (frequency and proportion). Graphical presentations, e.g. describing the change over time, will be used as appropriate, and individual patient data will be listed.

The primary and secondary endpoints (change in DLQI, Patient's Global Assessment of Skin Pain (NRS), EQ-5D VAS score and WPAI:SHP at 4, 12 and 24 weeks) will be analyzed using paired samples t-tests or non-parametric methods such as Wilcoxon signed rank test as appropriate.

HiSCR is a dichotomous response variable which will be analysed descriptively presenting proportion HiSCR with binomial exact 95% confidence interval.

The change at 12 weeks will be of primary interest.

Visit windows regarding 4, 12 and 24 weeks assessments following first dose of Adalimumab will decide the validity of assessment.

•	Baseline	Last assessment before first dose of Adalimumab
•	4 weeks	Day $(4*7)$ - $(3*7) \ll 4$ weeks \ll Day $(4*7)$ + $(3*7)$

•	12 weeks	Day (12*7)-(4*7)	<= 12 weeks <= Day (12*7)+(4*7)
•	24 weeks	Day (24*7)-(7*7)	<= 24 weeks <= Day (24*7)+(7*7)

Assessments outside these visit windows will not be part of input for summaries by visit. Such assessments will only be presented in listings.

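### The only specified SAE summary counts yes answers by visit, so no planned table gives patients with an SAE, events, severity or relationship

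*SAP*

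**What the plan says.** SAP 5.3 names serious adverse events as a safety endpoint. Besides the reporting period, it describes only a visit item: "In the CRF the response to the following question is registered at 4, 12 and 24 week visits", followed by the question whether any SAE has occurred since the last visit. SAP 6.5 then gives the whole safety analysis: "Responses to the CRF question 'Has any SAE(s) occurred since last visit?' will be summarized descriptively for the 4, 12 and 24 week visits". Protocol 9.7 says nothing about summarising SAEs.

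SAP 6.2 adds general wording. Descriptive statistics are to be given for safety variables as appropriate, individual data are to be listed, and "Categorical data will be summarised in frequency tables showing number of patients, frequency and percentage of occurrence by treatment group".

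The protocol asks for much more than a visit answer:

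- 11.1.2 gives definitions to "rate the severity for any adverse event being collected as an endpoint/data point in the study and for all serious adverse events".
- 11.1.3 states: "The following definitions will be used to assess the relationship of the adverse event to the use of product".
- 11.1.5 has the site notify the sponsor "within 24 hours of the site being made aware of the event by entering the serious adverse event" data into the electronic data capture (EDC) system. Fax or e-mail is used if that system is not yet accessible or is down.
- 11.1.4 runs SAE collection from consent "until 30 days or 5 half-lives following the intake of the last dose of physician-prescribed treatment".

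**The concern.** The study requires a record for each SAE but plans to summarise a yes/no answer given at three visits. The basic safety statement for a single-arm study is how many treated patients had at least one SAE, how many events there were, how many were fatal, and how many had a reasonable possibility of relationship. No planned table provides any of these. The one summary that is planned can also undercount, because it depends on a visit form being completed after the event. What is at stake is the completeness and readability of the safety section of the report. No effectiveness endpoint is affected.

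**Working it through.** The documents give no SAE rate, so there is no planned SAE figure to reproduce. The inputs are three visits (SAP 5.3, 6.5), 50 evaluable patients and drop-out of about 5% after 12 weeks (SAP 3.2.1; Protocol 9.5). All yes counts below are assumed for illustration.

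**1. What the specified summary yields.** Applying SAP 6.2 to the question in SAP 6.5 gives, for each visit, the number and percentage of patients answering yes. Call the counts y4, y12 and y24.

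**2. Distinct patients.** The same patient may answer yes at more than one visit. Among patients with a summarised yes:

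- fewest = max(y4, y12, y24)
- most = min(50, y4 + y12 + y24)

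The sum cannot exceed three times the largest count, so the range is at most threefold.

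**3. Events.** One yes can cover several SAEs. If each yes refers to at least one event new since the last visit, events ≥ y4 + y12 + y24, with no upper limit.

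| Assumed y4, y12, y24 | Distinct patients | % of 50 | Events |
|---|---|---|---|
| 1, 1, 1 | 1 to 3 | 2% to 6% | at least 3 |
| 2, 2, 2 | 2 to 6 | 4% to 12% | at least 6 |
| 3, 3, 3 | 3 to 9 | 6% to 18% | at least 9 |

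For the middle row, the exact 95% interval is 0.5% to 13.7% if there were 2 patients and 4.5% to 24.3% if there were 6.

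**4. Severity and relationship.** Neither is part of the visit answer, so no by-visit count can show them.

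**5. SAEs with no later form.** If a patient completes no visit form after an SAE, there is no answer to count. Drop-out of 0.05 × 50 = 2.5 suggests 2 to 3 patients without a week 12 form. How many of them would have had an SAE is unknown. An SAE that causes a single missed visit can still be picked up at the next one.

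**6. SAEs after week 24.** The last question is asked at the week 24 visit, planned for day 168. Treatment is routine care and need not stop then. Under the 30-day limit, a last dose on day 168 keeps SAE collection open to day 168 + 30 = 198. The documents give no half-life, so the other limit cannot be placed in days. An SAE in this period is reportable but falls after the last visit question.

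**The case against.** The strongest reply is that SAP 6.2 already covers this. SAEs are a named safety endpoint, severity and relationship are categorical, and 6.2 promises descriptive statistics for safety variables and listings of individual data. With about 50 patients, a reader could count from a listing. In addition, a sponsor physician reviews all collected SAEs (Protocol 9.8), reasons for withdrawal are listed (SAP 6.3.1), and product complaints associated with adverse events go into the study summary (Protocol 11.2.2). Safety is not a stated objective, and Protocol 11.1.5 describes the safety profile as well established.

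Much of this stands. It rules out the inference that SAEs are lost, that the SAP forbids a proper table, or that the report could not state how many patients had one. What remains is narrower: 6.2 is generic and leaves the choice open, 6.5 names a specific method, and that method is the weaker one. A report could follow the SAP fully and contain no patient-level SAE table.

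Three other stronger readings also fail. A reader might infer that every fatal SAE is left out, but the documents do not say whether the visit item is completed after a death. A reader might take the range in step 2 as bounding all patients with an SAE. It bounds only those with a summarised yes, and the true number can be higher because of steps 5 and 6. A reader might also infer that the visit windows in SAP 6 remove some answers, but the SAP does not say whether they apply to this question, and nothing here relies on that.

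**Conclusion.** The point holds as a minor one. SAP 6.5 bases its only specified SAE summary on visit answers and not on the SAE records that the protocol requires. The summary leaves the number of distinct patients with a summarised yes uncertain by up to a factor of three. It gives only a lower limit for events, says nothing on severity or relationship, and can undercount. The actual effect on the reported SAE frequency is unknown, because the documents give no SAE rate.

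This rests on reading 6.5 as written, and on the inference from Protocol 11.1.2, 11.1.3 and 11.1.5 that severity and relationship are held with each SAE report. The weight is modest because the events remain in the EDC system and the listings, and no stated objective or effectiveness result depends on them.

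**What to change.** Reword SAP 6.5 so that the SAE summary uses all reported SAE records, meaning EDC entries plus any fax or e-mail reports, in patients given at least one dose, up to a stated data cut-off. A cut-off is needed because collection follows the last dose of routine-care treatment, while site access to the eCRF ends with site participation (Protocol 9.6).

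- **One table:** number and percentage of patients with at least one SAE, number of events, deaths, severity and relationship. State the denominator, because the safety set in SAP 4.4 requires follow-up safety data without saying whether an SAE report alone counts. Show events after the week 24 visit separately, marked as possibly incomplete.
- **One listing:** all SAEs, including those before first dose.
- **Visit question:** keep it as a check that each yes has a matching SAE record.

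The cost is SAP wording, one table and one listing. Up to the end of site participation no new data collection is needed. The downside is less complete capture after week 24, which the cut-off and the separate display make visible but do not remove.
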